4. STUDY POPULATION

The inclusion and exclusion criteria for enrolling subjects in this study are described in the following 2 subsections. If there is a question about the inclusion or exclusion criteria below, the investigator should consult with the appropriate sponsor representative before enrolling a subject in the study. Waivers are not allowed. Eligibility criteria for subjects in the placebo arm who crossover to active treatment with apalutamide (in the event of a positive study result and unblinding) are described in [Attachment 6](#).

4.1. Inclusion Criteria

Each potential subject must satisfy all of the following criteria to be enrolled in the study.

1. Criterion modified per Amendment 1
 - 1.1 Subject must be a man ≥ 18 years of age (or the legal age of consent in the jurisdiction in which the study is taking place)

-
2. Criterion modified per Amendment 1
 - 2.1. Diagnosis of prostate adenocarcinoma as confirmed by the investigator
 3. Criterion modified per Amendment 1
 - 3.1. Metastatic disease documented by ≥ 1 bone lesion(s) on Technetium-99m (^{99m}Tc) bone scan. Subjects with a single bone lesion must have confirmation of bone metastasis by computed tomography (CT) or magnetic resonance imaging (MRI).
 4. Criterion modified per Amendment 1
 - 4.1. ECOG PS grade of 0 or 1 ([Attachment 2](#))
 5. Criterion modified per Amendment 1
 - 5.1. Androgen deprivation therapy (ie, medical or surgical castration) must have been started ≥ 14 days prior to randomization. Subjects who start a GnRH agonist ≤ 28 days prior to randomization will be required to take a first-generation anti-androgen for ≥ 14 days prior to randomization. The anti-androgen must be discontinued prior to randomization.
 6. Criterion modified per Amendment 1
 - 6.1. Subjects who received docetaxel treatment must meet the following criteria:
 - a. Received a maximum of 6 cycles of docetaxel therapy for mHSPC
 - b. Received the last dose of docetaxel ≤ 2 months prior to randomization
 - c. Maintained a response to docetaxel of stable disease or better, by investigator assessment of imaging and PSA, prior to randomization
 7. Criterion modified per Amendment 1
 - 7.1. Be able to swallow whole study drug tablets
 8. To avoid risk of drug exposure through the ejaculate (even men with vasectomies), subjects must use a condom during sexual activity while on study drug and for 3 months following the last dose of study drug. Donation of sperm is not allowed while on study drug and for 3 months following the last dose of study drug.
 9. Each subject must sign an informed consent form (ICF) indicating that he understands the purpose of and procedures, required for the study, and is willing to participate in the study. Subject must be willing and able to adhere to the prohibitions and restrictions specified in this protocol (see Section [4.3](#)).
 10. Other allowed prior treatment for mHSPC:
 - a. Maximum of 1 course of radiation or surgical intervention; radiation therapy for metastatic lesions must be completed prior to randomization

- b. ≤ 6 months of ADT prior to randomization
11. Allowed prior treatments for localized prostate cancer (all treatments must have been completed ≥ 1 year prior to randomization)
- a. ≤ 3 years total of ADT
 - b. All other forms of prior therapies including radiation therapy, prostatectomy, lymph node dissection, and systemic therapies

4.2. Exclusion Criteria

Any potential subject who meets any of the following criteria will be excluded from participating in the study.

1. Pathological finding consistent with small cell, ductal or neuroendocrine carcinoma of the prostate
2. Known brain metastases
3. Criterion modified per Amendment 1
 - 3.1. Lymph nodes as only sites of metastases
4. Criterion modified per Amendment 1
 - 4.1. Visceral (ie, liver or lung) metastases as only sites of metastases
5. Criterion modified per Amendment 1
 - 5.1. Other prior malignancy (exceptions: adequately treated basal cell or squamous cell skin cancer, superficial bladder cancer, or any other cancer in situ currently in complete remission) ≤ 5 years prior to randomization
6. Clinical laboratory values during the Screening Phase:
 - a) hemoglobin < 9.0 g/dL
 - b) neutrophils $< 1.5 \times 10^9/L$
 - c) platelets $< 100 \times 10^9/L$
 - d) total bilirubin $> 1.5 \times$ upper limit of normal (ULN) [NOTE: in subjects with Gilbert's syndrome, if total bilirubin is $> 1.5 \times$ ULN, measure direct and indirect bilirubin and if direct bilirubin is $\leq 1.5 \times$ ULN, subject may be eligible]
 - e) alanine aminotransferase (ALT) or aspartate aminotransferase (AST) $> 2.5 \times$ ULN
 - f) serum creatinine $> 2.0 \times$ ULN
 - g) serum albumin < 3.0 g/dL
7. Criterion modified per Amendment 1

-
- 7.1. Criterion modified per Amendment 4
 - 7.2. Prior treatment with other next generation anti-androgens (eg, enzalutamide), CYP17 inhibitors (eg, abiraterone acetate), immunotherapy (eg, sipuleucel-T), radiopharmaceutical agents or other treatments for prostate cancer except those listed in Inclusion Criteria #5.1, #6.1, #10, and #11 (see also Section 8.2)
 8. Criterion modified per Amendment 1
 - 8.1. Initiation of treatment with a bisphosphonate or denosumab for the management of bone metastasis ≤ 28 days prior to randomization
 9. Criterion modified per Amendment 1
 - 9.1. Medications known to lower the seizure threshold must be discontinued or substituted ≥ 28 days prior to randomization (see Section 8.2)
 10. Criterion modified per Amendment 1
 - 10.1. Administration of other investigational therapeutic agents, blood product support, growth factor support or invasive surgical procedure (not including surgical castration) ≤ 28 days prior to randomization or currently enrolled in an investigational study
 11. Current or prior treatment with anti-epileptic medications for the treatment of seizures. History of seizure or condition that may predispose to seizure (including, but not limited to prior cerebrovascular accident, transient ischemic attack, or loss of consciousness within 1 year prior to randomization; brain arteriovenous malformation; or intracranial masses such as a schwannoma or meningioma that is causing edema or mass effect).
 12. Criterion modified per Amendment 1
 - 12.1. Current evidence of any of the following:
 - a) Severe/unstable angina, myocardial infarction, symptomatic congestive heart failure, uncontrolled hypertension, clinically significant arterial or venous thromboembolic events (eg, pulmonary embolism), or clinically significant ventricular arrhythmias ≤ 6 months prior to randomization
 - b) Gastrointestinal disorder affecting absorption
 - c) Active infection requiring systemic therapy such as human immunodeficiency virus (HIV)
 - d) Active or symptomatic viral hepatitis or chronic liver disease; ascites or bleeding disorders secondary to hepatic dysfunction
 13. Subject has known allergies, hypersensitivity, or intolerance to apalutamide or its excipients (refer to Investigator's Brochure)
 14. Any condition or situation that in the opinion of the investigator, would preclude participation in this study
-

4.3. Prohibitions and Restrictions

Potential subjects must be willing and able to adhere to the following prohibitions and restrictions during the course of the study to be eligible for participation:

1. Refer to Section 8 for details regarding prohibited and restricted therapy during the study
2. If the subject is engaged in sexual activity with a partner, a condom is required.

If the subject is engaged in sexual activity with a woman of childbearing potential, a condom is required along with another effective contraceptive method consistent with local regulations regarding the use of birth control methods for subjects participating in clinical studies and their partners. Highly effective forms of contraception include:

- established use of oral, injected or implanted hormonal methods of contraception; placement of an intrauterine device (IUD) or intrauterine (IUS) system;
 - barrier methods: condom with spermicidal foam/gel/film/cream/suppository or occlusive cap (diaphragm or cervical/vault caps) with spermicidal foam/gel/film/cream/suppository;
 - vasectomy
3. Two highly effective forms of contraception are required during the Treatment Phase and for 3 months after the last dose of study drug.

5. TREATMENT ALLOCATION AND BLINDING

Treatment Allocation

Procedures for Stratification and Randomization

Subjects will be stratified by Gleason score at diagnosis (≤ 7 versus >7), region (North America [NA] and European Union [EU] versus Other Countries), and prior docetaxel use (Yes versus No). Subjects will be randomly assigned to the active or control group in a 1:1 ratio. The randomization will be balanced by using randomly permuted blocks. The interactive web response system (IWRS) will assign a unique treatment code, which will dictate the treatment assignment and matching study drug kit for the subject. The requestor must use his own user identification and personal identification number when contacting the IWRS, and will then give the relevant subject details to uniquely identify the subject.

Blinding

The investigator will not be provided with randomization codes. The codes will be maintained within the IWRS, which has the functionality to allow the investigator to break the blind in the event of an emergency for an individual subject.

Under normal circumstances, the blind should not be broken until completion of the study or the IDMC recommendation for unblinding is accepted by the sponsor. Otherwise, the blind should be broken only if the specific course of action for a safety issue would be dictated by knowing the treatment status of the subject. In such cases, the investigator may in an emergency determine the identity of the treatment by contacting the IWRS. It is recommended that the investigator contact the sponsor or its designee if possible to discuss the particular situation, before breaking the blind. Telephone contact with the sponsor or its designee will be available 24 hours per day, 7 days per week. In the event the blind is broken, the sponsor must be informed as soon as possible. The date, time, and reason for the unblinding must be documented by the IWRS, in the appropriate section of the electronic case report form (eCRF), and in the source document. The documentation received from the IWRS indicating the code break must be retained with the subject's source documents in a secure manner.

Unblinding may also be performed after the subject discontinues from the Treatment Phase of study because of radiographic progression and the investigator feels this information is essential to determine the next course of therapy. Unblinding a subject for this situation may only take place after discussion with the sponsor's medical officer. Subjects who have had their treatment assignment unblinded should be discontinued from the Treatment Phase and entered in the Follow-up Phase.

In general, randomization codes will be disclosed fully only if the study is completed and the clinical database is closed. However, if an interim analysis is specified, the randomization codes and, if required, the translation of randomization codes into treatment and control groups will be disclosed to those authorized and only for those subjects included in the interim analysis.

6. DOSAGE AND ADMINISTRATION

6.1. Study Drug Administration

Study drug will be administered on a continual basis, but for the purpose of scheduling the study assessments and treatment compliance, a treatment cycle is defined as 28 days. Subjects will be randomly assigned in a 1:1 ratio to receive either apalutamide or matching placebo

- JNJ-56021927 (apalutamide) 240-mg (4 x 60-mg tablets); taken orally once daily with or without food or
- Placebo (4 tablets); taken orally once daily with or without food

If a dose of apalutamide (or placebo) is missed it should be omitted and will not be made up or taken with the next dose the following day. Please refer to the pharmacy manual/study-site investigational product manual for further details. Study drug administration must be captured in the source documents and the eCRF.

See the Time and Events Schedule for details on timing of drug administration during PK collection.

6.2. ADT Administration

All subjects who did not undergo surgical castration, will receive and remain on a stable regimen of ADT. The choice of the GnRHa (agonist or antagonist) will be at discretion of the Investigator. Dosing (dose and frequency of administration) will be consistent with the prescribing information. For subjects who did not undergo surgical castration, concurrent treatment with a GnRHa must be documented in the eCRF.

6.3. Toxicity and Rash Management

Table 1 summarizes apalutamide/placebo dose modifications for drug-related toxicities. Dose modifications for drug-related rashes are summarized in Table 2. Once the dose is reduced for drug-related toxicities, a re-escalation of the dose should be discussed with the sponsor.

Table 1: Dose Modifications of Apalutamide/Placebo (except for rash, if rash occurs, see Table 2)

Severity	Number of apalutamide/placebo tablets
Grade 1 or 2	No change or hold until return to baseline
≥Grade 3	Hold until Grade 1 or baseline, resume at full dose
Recurrence ≥Grade 3	Hold until Grade 1 or baseline; 2 dose reductions are allowed for recurrent treatment-related toxicity (180 mg [3 tablets]) and 120 mg [2 tablets]). Discontinue if toxicity persists after 2 dose reductions.
First occurrence of seizure of any grade or Grade 4 neurotoxicity	Discontinue
Note: Adverse events are graded according to NCI-CTCAE Version 4.03	

If the skin rash has any component of desquamation, mucosal involvement, or pustules, stop dosing with apalutamide/placebo, refer to dermatology for evaluation, and a skin biopsy is recommended (in addition to the interventions listed in Table 2) (and complete the skin rash eCRF). If the skin rash is Grade 3 or higher, asking the subject to consent to documentation by a photograph and further evaluation by dermatology should also be considered (and complete the skin rash eCRF). Also complete the skin rash eCRF if the skin rash leads to permanent discontinuation of study drug.

Table 2 Management of Drug-Related Rash

Severity	Intervention
Grade 1	
 • Continue apalutamide/placebo at current dose • Initiate dermatological treatment^a 
 ○ Topical steroid cream AND ○ Oral antihistamines • Monitor for change in severity^a
Grade 2 (or symptomatic Grade 1)^b	
 • At investigator discretion, hold apalutamide/placebo for up to 28 days • Initiate dermatological treatment^a 
 ○ Topical steroid cream AND ○ Oral antihistamines • Monitor for change in severity^a 
 ○ If rash or related symptoms improve, reinitiate apalutamide/placebo when rash is Grade ≤ 1. Consider dose reduction at 1 dose level reduction.
Grade ≥ 3^d	
 • Hold apalutamide/placebo for up to 28 days • Initiate dermatological treatment^a 
 ○ Topical steroid cream AND ○ Oral antihistamines AND ○ Consider short course of oral steroids • Reassess after 2 weeks (by site staff), and if the rash is the same or has worsened, initiate oral steroids (if not already done) and refer the subject to a dermatologist 
 ○ Reinitiate apalutamide/placebo at 1 dose level reduction^c when rash is Grade ≤ 1. ○ If the dose reduction will lead to a dose less than 120 mg, the study drug must be stopped (discontinued) • If after 28 days, rash has not resolved to Grade ≤ 1, contact the sponsor to discuss further management and possible discontinuation of study drug

Note: Rash may be graded differently according to the type of rash and associated symptoms. For example, maculopapular rash is graded by body surface area covered and not severity of the rash. Please consult NCI-CTCAE Version 4.03 for specific grading criteria for other types of rash.

^{a.} Obtain bacterial/viral cultures if infection is suspected

^{b.} Subject presents with other rash-related symptoms such as pruritus, stinging, or burning

^{c.} If a subject previously started oral corticosteroids continue for at least 1 week after resumption of reduced dose of apalutamide/placebo. If the proposed total oral steroid use will exceed 28 days, contact the sponsor.

^{d.} If there is blistering or mucosal involvement, stop apalutamide/placebo dosing immediately and contact the sponsor

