- The investigator believes that for safety reasons (eg, AE) it is in the best interest of the subject to discontinue study treatment

All attempts to obtain imaging studies at the time of treatment discontinuation or EOT Visit should be made to assess for radiographic progression. Study drug will be continued for subjects who have increasing PSA values in the absence of radiographic or clinical progression. Although serial PSA measurements will be performed in this study, progression or change in PSA values should not be used as the lone indicator for disease progression or treatment discontinuation. If a

subject discontinues study drug, but does not withdraw consent for follow-up, scheduled assessments should continue according to the Follow-up Phase in the Time and Events Schedule.

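### Section 6.3 does not clearly require a stop for a Grade 1 or 2 rash with blistering alone

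*Protocol*

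**What the plan says.** Section 6.3 handles rash in two places.

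- **The paragraph before Table 2.** "If the skin rash has any component of desquamation, mucosal involvement, or pustules, stop dosing with apalutamide/placebo". No grade is attached. The same sentence asks for dermatology referral, recommends a skin biopsy and calls for the skin rash eCRF page. It says these steps come on top of the Table 2 interventions.
- **Table 2, by grade.** Grade 1: "Continue apalutamide/placebo at current dose". Grade 2 or symptomatic Grade 1: "At investigator discretion, hold apalutamide/placebo for up to 28 days". Grade 3 or higher: "Hold apalutamide/placebo for up to 28 days", with restart one dose level lower once the rash is back to Grade 1 or less, and discontinuation if that would take the dose under 120 mg.

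Three notes to the table matter here.

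- Footnote d: "If there is blistering or mucosal involvement, stop apalutamide/placebo dosing immediately and contact the sponsor". Its marker is on the Grade 3 or higher label only.
- Footnote b explains a symptomatic rash: "Subject presents with other rash-related symptoms such as pruritus, stinging, or burning".
- The general note warns that "maculopapular rash is graded by body surface area covered and not severity of the rash" and refers sites to NCI-CTCAE Version 4.03 for other rash types.

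Table 1 offers no fallback, because its title excludes rash.

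**The concern.** Footnote d puts blistering and mucosal involvement side by side as reasons to stop at once. The paragraph makes mucosal involvement a stop at any grade and does not mention blistering. Nothing in the protocol explains why one of the pair should be an explicit stop at every grade and the other only where the footnote is marked. It looks like an omission.

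A site that follows the Grade 1 row literally would keep dosing a subject who has a feature that the protocol elsewhere treats as an immediate stop. More than the stop goes with the omission. Low-grade blistering alone does not trigger the paragraph's dermatology referral or its skin rash eCRF page, so the event may also be less fully documented.

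In the earlier Phase 3 study summarised in Section 1.1.2.1 (ARN-509-003), most skin rash was Grade 1 or 2. The two rows with the gap are therefore likely to be the ones most used.

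**Working it through.** There is no planned figure to reproduce. The check is to take each warning feature alone, at each row of Table 2, and ask which text requires a stop.

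| Feature alone | Grade 1 | Grade 2 or symptomatic Grade 1 | Grade 3 or higher |
|---|---|---|---|
| Desquamation | Stop (paragraph) | Stop (paragraph) | Stop (paragraph) |
| Pustules | Stop (paragraph) | Stop (paragraph) | Stop (paragraph) |
| Mucosal involvement | Stop (paragraph) | Stop (paragraph) | Stop (paragraph and footnote d) |
| Blistering | Row says continue | Row says hold is discretionary | Stop (footnote d) |

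1. There are 4 features × 3 rows = 12 combinations.
2. The paragraph covers 3 features × 3 rows = 9.
3. Footnote d, applied where its marker sits, adds blistering at Grade 3 or higher: 9 + 1 = 10.
4. That leaves 12 − 10 = 2 combinations with no clear mandatory stop: blistering alone in the Grade 1 row, and blistering alone in the Grade 2 or symptomatic Grade 1 row.

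This count shows where the gap lies. It does not measure risk.

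The remaining texts that might close the two cells were then checked.

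- **Footnotes a and b**, the only ones marked in the low-grade rows. Footnote a concerns cultures when infection is suspected. Footnote b gives examples only, so a blistering Grade 1 rash with symptoms could be moved up a row, but the hold in that row is discretionary.
- **The note on grading.** For maculopapular rash at least, the grade reflects area covered, so a low grade does not by itself rule out a warning feature.
- **Section 10.2.** Treatment must stop if "The investigator believes that for safety reasons (eg, AE) it is in the best interest of the subject to discontinue study treatment". This depends on judgement and does not name blistering.
- **Section 9.1.3.** Investigators use the accumulating clinical data to decide on dose changes and discontinuation. This is also judgement.

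None of these turns a low-grade blistering rash into an explicit mandatory stop.

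**The case against.** The strongest reply is that footnote d carries no grade condition of its own. Its limit to Grade 3 or higher comes only from where the marker is placed. It also names mucosal involvement, which is already a stop at any grade, so it can be read as a general reminder of warning signs. This stands in part. A reader might infer that the protocol restricts the blistering stop to Grade 3 or higher. The documents do not go that far; they leave Grade 1 and 2 unclear. But a footnote ordinarily applies where it is marked, and a safety stop should not depend on a site ignoring that.

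Second, the investigator is free to stop. Sections 9.1.3 and 10.2 allow it, and both low-grade rows ask for monitoring for a change in severity. This stands fully: a reader should not infer that sites must keep dosing whatever they see, or that Section 10.2 is the sole safeguard. What is missing is the instruction, and for the other three features the protocol did not leave the matter to discretion.

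Third, the practical case needs a blistering rash graded 1 or 2. Grading of rash types other than maculopapular rests on NCI-CTCAE Version 4.03, which is not reproduced in the protocol, and neither document says how many rashes blistered. This stands: no frequency can be given.

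Fourth, a marker on another row could have been lost when the PDF was read. This is unlikely, because markers a to d all survive elsewhere in the table, but it cannot be excluded. If footnote d were marked on every row, only the mismatch between list and footnote would remain.

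A reader might also infer that the paragraph and the table conflict for desquamation, pustules and mucosal involvement at low grade. The low-grade rows do not point back to the paragraph, but it stands directly before the table in the same section and is best read as taking precedence.

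**Conclusion.** The point holds as a gap in the mandatory instruction. For a Grade 1 or 2 rash with blistering alone, Section 6.3 does not clearly require a stop, and the rows as written say to continue or to hold at discretion. It is minor. Two of the 12 feature-by-row combinations are affected, the number of subjects is unknown and probably small, and no efficacy analysis changes.

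The conclusion rests on two assumptions: that footnote d is marked only on the Grade 3 or higher row, as the text shows, and that a blistering rash can be graded 1 or 2. Confidence is high on the wording. The clinical consequence cannot be sized from the documents.

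**What to change.** 1. Add blistering to the any-grade stop list in the Section 6.3 paragraph.
2. Attach footnote d to every row of Table 2, or to the table title, and add: *Applies at every grade. At Grade 1 or 2 it takes precedence over the row's instruction to continue or to hold at discretion.*
3. Leave the Grade 3 or higher row as it is, with its mandatory one-level reduction and 120 mg floor. The override should be confined to Grade 1 and 2. An override of every row's dosing instruction that left the restart dose open would remove the required reduction for the most severe rashes.

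Restart after a low-grade stop can be settled in the sponsor contact that footnote d already requires. The paragraph's biopsy recommendation need not be extended to blistering, and the revised sentence can say so.

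The cost is a wording change in one paragraph and one footnote, with no new analysis. The downside is a few more dose interruptions, sponsor contacts, dermatology referrals and skin rash eCRF pages for low-grade rash.
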